6.0 STUDY INTERVENTION(S)

6.1 Investigational/Test Device

The PureWickTM System includes the PureWickTM Female External Catheter and the PureWickTM Urine Collection System. The PureWickTM Female External Catheter (PureWickTM FEC) is marketed in both the United States and Europe. In the U.S. PureWickTM FEC is a Class I, 510(k) exempt device. In Europe, the PureWickTM FEC is a Class I, CE marked, non-sterile device.

The PureWick[™] FEC is intended for non-invasive urine output management in female patients. The PureWick[™] FEC (Figure 1) is a flexible, contoured external catheter that is positioned against the area where urine exits the female body. The PureWick[™] FEC will be connected to the PureWick[™] Urine Collection System (PUCS) via connector tubing. The PUCS uses suction (not felt by the user) to pull voided urine through the device. Urine continues through vinyl tubing until it reaches a collection canister, away from the body. The PureWick[™] FEC and PUCS will be used according to the IFU.

6.2 Pre-placement Procedure

Prior to placing the PureWick TM FEC, perineal care should be performed, and skin should be assessed for integrity.

Figure 1: PureWickTM Female External Catheter

Continuous low pressure suction at the base removes urine.

Figure 2: PureWick[™] Urine Collection System

All PureWick[™] FECs and PUCS will be shipped directly to the study site from regular commercial stock. Access to the devices will be limited to study staff and will only be used by study participants who have provided written informed consent.

6.3 Control Device/Standard of Care

The Hollister[®] Female Urinary Pouch External Collection Device will be used as a comparator for this study. The urinary collection pouch with a skin barrier is suitable for non-ambulatory females with urinary incontinence. It is designed to be emptied and should be attached to a drainage bag. The FUP is made with hydrocolloid skin adhesive and polymer/copolymer plastics.

6.4 Pre-placement Procedure

To prepare the skin prior to placing the Hollister® FUP, the genital area should be washed with a mild soap and water and pubic hair trimmed. After drying the area thoroughly, the skin that will be in contact with the skin barrier may be wiped with a skin protective wipe if desired.

The pre-cut opening on the skin barrier can be modified so that it will encompass the urinary and vaginal orifices by cutting the opening with scissors.

If desired, barrier paste may be placed on the edge of the skin barrier that will adhere to areas where the skin surface is creased or uneven prior to placement.

Figure 3: Hollister® Female Urinary Pouch One-System and Bedside Drainage Bag

All Hollister[®] Female Urinary Pouch External Collection Devices will be shipped directly to the study site from regular commercial stock. Access to the devices will be limited to study staff and will only be used by study participants who have provided written informed consent.

6.5 Ancillary Devices/Products

- PureWick[™] replacement kit (PWKIT03) (US) and (PWKIT03E) (EU)
- Absorbent under-pads will be used to collect and measure urine leakage.
- Medium/Large sealing plastic bags
- Medical triangular graduated cylinders, 1000mL
- Commercially available scales will be used to weigh under-pads and mesh underwear. both before and after use to calculate urine capture rates.
- Bedside urine collection bags to capture outputs from the Hollister FUP
- Bedside urine bag holder
- Mesh Underwear
- PPE (gloves, chux)
- Barrier Paste
- Wipes
- Micropore tape
- Hair trimmers/clippers

6.6 Device Labeling

Commercial products will be supplied as labeled by the manufacturer. The test device and comparator products shall be labeled in accordance with regulatory requirements, including the following statement, "CAUTION - Investigational Device. Limited by Federal (or United States) law to investigational use." for the products used in the US, and with the following statement "exclusively for clinical investigation" for the devices used in France.

6.7 Treatment Allocation and Measures to Minimize Bias

Known foreseeable factors that could potentially compromise the outcome of the investigation or interpretation of the results or introduce bias into the study are delineated in this section.

This is an open label, cross-over study in which each subject acts as her own control and therefore, the difference in treatments is derived from a within-subject comparison. This allows for better control of potential confounders and removes the inter-subject variability from the comparison between treatment groups. In addition, the study design includes a required washout period between treatment phases to minimize the impact of carry-over effect.

Standardized questionnaires and data collection tools will be used to assess participant preference and to document study findings, respectively. As training level and device experience could be a foreseeable factor that could impact study outcomes, standardized instructional videos will be used to train all participants on device use.

6.8 Randomization

Subjects will be randomized 1:1 to the two sequences of treatment (using PureWickTM FECs in phase 1 and Hollister[®] Female External Pouch in phase 2, or the reversed order). This design allows the evaluation of elements such as the carryover effect, period effect, and sequence effect. To begin treatment phase in either the U.S. or France, using a prepared randomization schedule participants will be randomized 1:1 to use either PureWickTM FEC in phase 1 and Hollister[®] FUP in phase 2, or vice versa. Block randomization will be carried out using a fixed block size and stratified by investigational site and geography.

6.8.1 Blinding/Masking

Not applicable. This is an open-label study.

6.8.2 **Procedures for Unblinding**

Not applicable.

7.0 STUDY PROCEDURES AND ASSESSMENTS

Study procedures and their timing are summarized in the Schema (Section 1.2). Protocol waivers or exemptions are not allowed. Adherence to the study design requirements, including those specified in the SoA, is essential and required for study conduct.

All screening evaluations must be completed and reviewed to confirm that potential participants meet all eligibility criteria. The investigator will maintain a screening log to record details of all participants screened and to confirm eligibility or record reasons for screening failure, as applicable.

7.2 Screening and Enrollment

7.2.1 Informed Consent

The Principal Investigator or their designee will explain the study to the participant, answer all the participant's questions, and obtain written or electronic informed consent before the collection of any study data or performance of any study procedures in accordance with article 63 of the European Medical Device Regulations respectively CFR Parts 50 and 56 and any other applicable laws and regulations. The original copy of the consent will be retained with the participant records and a copy will be provided to the participant.

7.2.2 Eligibility

The participant's eligibility (inclusion/exclusion criteria) for study participation will be confirmed by the PI or designee (via on site or virtual visit (U.S. only)) per investigational site policy) and documented on the appropriate electronic case report form (eCRF). Participant baseline and demographic information, including, but not limited to age, sex assigned at birth, primary diagnosis, medical history, Katz ADL Index score and incontinence-specific information will be collected and recorded after informed consent is obtained prior to device use.

Participants who fail to meet eligibility criteria due to an exclusionary criterion that is temporary in nature and may resolve over time (e.g., active infection, open wound, etc.) can be rescreened at the PI's discretion.

7.2.3 Enrollment/ Assignment of Participant Number

Participants who sign an informed consent will be considered enrolled in this study.

A unique identification number will be given to study participants. Participant numbers will be assigned in sequential order. The participant number will consist of six digits. The first three digits will designate the site number and the last three digits will designate the participant number in sequential order.

7.2.4 Randomization

Investigational sites will receive the randomization envelopes that are numbered in sequential orders. Within each randomization envelope, a treatment assignment card will be enclosed indicating which device to be used for each treatment phase. The

randomization envelope will be opened when all eligibility criteria are confirmed, and consent has been obtained. Randomization envelopes should be opened in sequential order. The treatment assignment card will be filed in the participant's record to serve as documentation. Participant randomization numbers will be captured in EDC.

7.2.5 Home Nurse Introduction

The Principal Investigator or their designee will introduce enrolled participants to the nurse that will conduct daily home visits (either in person or virtually).

Nurse and participant will arrange the baseline visit. Once a baseline visit has been scheduled, the site coordinator/Pharmacist will reach out to Marken and setup study device shipment from clinical site to the Participant's home.

7.2.6 Day 1 - Baseline Assessments

This part of the study is to assess if the participants are eligible to begin treatment per assigned treatment schedule. During the baseline assessment urine output measurements will not be taken.

The nurse will collect nighttime routine (e.g., sleep position) and visually assess for any existing signs of irritation in the perineal area, using the Draize Scale Skin Scoring system.

If Skin Score is Greater than 0:

- 1. Participant is not eligible to begin treatment on that day.
- 2. Baseline visit can be rescheduled at the nurse's discretion within 2-4 weeks.
- 3. If the skin score of 0 is not achieved within 4 weeks from the original baseline visit, the participant will not be eligible for treatment.
- 4. Nurse will notify PI and Site staff will complete appropriate eCRFs.

If Skin Score is 0:

- 1. Nurse will have participant complete Baseline N-QOL & PROMIS Sleep Disturbance assessment.
- 2. Nurse will confirm treatment assignment.
- 3. Nurse will provide device and procedure training via standardized product training video.
- 4. Once training is completed, nurse will ensure the participant have all the supplies prepped for the first night of device wear.
- 5. Nurse will pre-weigh and document weight of sealed bed pad in bag
- 6. If assigned to PureWickTM treatment phase, nurse will pre-weigh and document weight of canister before use.
- 7. If assigned to Hollister FUP treatment phase, nurse will pre-weigh and document weight of the graduated cylinder.
- 8. If applicable, nurse will pre-weigh and document weight of mesh underwear in bag.

9. Nurse will confirm next day visit with participant.

7.2.7 Days 2-7

- 1. Prior to nurse visit, participants are expected to have placed the used night pads and mesh underwear (if applicable) in their respective labeled, pre-weighed sealed bag upon completion of sleep.
- 2. Nurse will weigh and document weight of night pads and mesh underwear (if applicable).
- 3. The nurse will weigh and document the captured urine.
 - For PureWickTM Treatment Phase the captured urine volume in the PW urine collection canister will be weighed and documented.
 - For Hollister_® FUP Treatment Phase the captured urine volume in the bedside urine bag will be emptied into a graduated cylinder, then weighed and documented.
- 4. The nurse will note any signs of skin irritation or injury and document the Draize Scale score*
- 5. If during the skin assessment a Draize score of 4 is documented on the skin irritation scale in any category, this must be recorded as an AE and will require participants to discontinue from the treatment phase; participant will immediately begin wash out period and complete N-QoL.
- 6. Nurse will pre-weigh and document weight of study supplies for next night use.
- 7. The nurse will confirm the next day visit.

* For safety assessment, see section 7.3

7.2.8 Day 8

- 1. Same procedures as days 2-7.
- 2. Participant to complete Day 8 PROMIS Sleep Disturbance assessment.

7.2.9 Days 9-14

1. Same procedures as days 2-7.

7.2.10 Day 15

- 1. Same procedures as days 2-7.
- 2. Participant to complete 2-week N-QOL assessment.
- 3. Participant to complete Day 15 PROMIS Sleep Disturbance assessment.

7.2.11 Days 16-21

1. Same procedures as days 2-7.

7.2.12 Day 22

- 1. Same procedures as days 2-7.
- 2. Participant to complete Day 22 PROMIS Sleep Disturbance assessment.

7.2.13 Days 23-28

1. Same procedures as days 2-7.

7.2.14 Day 29

- 1. Same procedures as days 2-7 with the exception of steps 6 and 7.
- 2. Participant to complete 4-week N-QOL assessment.
- 3. Participant to complete Day 29 PROMIS Sleep Disturbance assessment.
- 4. Participant to complete comfort and ease of use questionnaires.
- 5. If this day is the last day of phase 1 treatment for the participant, they will begin washout and prepare for phase 2 treatment.
- 6. If this day is the last day of phase 2 treatment for the participant, they will complete the study. Participant is to complete the End of Study Preference Survey.

7.2.15 Day 30

The participant will be asked to report any discomfort or voiding issues occurring within the first 24 hours after treatment phase completion or discharge from the study to the PI or sponsor. Skin assessments will also be conducted 24 hours after the participant completes the treatment phase and/or the study.

7.2.16 Days 29-42 (+14) Wash Out Period

Participant begins washout period of 2 weeks (not to exceed 4 weeks) between treatment phase 1 and treatment phase 2. At the completion of washout, the nurse will perform a rescreening of eligibility criteria before phase 2 treatment begins.

7.2.17 Treatment Phase 2

Same procedures as outline in sections 7.2 - 7.11.

7.3 Safety Assessments

7.3.1 Draize Scale

For each daily visit (described in 7.2-7.7), skin condition will be evaluated by nurses using the Draize scale (Table 1). Skin assessments will also be conducted 24 hours after the participant completes the study, either in person or virtually.

If during the skin assessment a Draize score of 4 is documented on the skin irritation scale in any category, it must be recorded as an AE and will require participants to discontinue from the treatment phase. Any other score on the skin irritation scale in any category may be recorded as an AE based on PI discretion.

To assess a potential AE identified during the home visit, the nurse will contact the PI or designee. The site will document the AE assessment on the appropriate CRF from and follow the AE until resolution. If the PI requests a follow up visit with the participant, this can be conducted on site or virtually per investigational site policy.

However, if the AE is not resolved during the treatment phase(s) within 4 weeks from the AE start date, the participant will be discontinued from the study.

Also, if during the skin assessment a Draize score of 2 or greater is documented for the device placement site, a photograph may need to be taken of the skin in the anatomical area of device application. The photo will be sent in a pseudonymized matter to the site, only the subject ID and the date when the picture was taken will be collected. These photographs will be shared with the Principal Investigator / Sub-Investigator, the Sponsor, and the study staff only and will be used for the Principal Investigator / Sub-Investigator / Sub-In

| Score | Erythema (redness) | Edema (swelling) | Bleeding |
|------------------------------|--|---|--|
| 0 | None | None | None |
| 1 ^{a} | Very slight (barely perceptible) erythema | Very slight (barely perceptible) skin surface rise | Just a visible spot of red |
| 2^a | Well-defined erythema | Well-defined skin surface rise (edges of area well-defined by definite raising) | A drop of red blood |
| 3 ^{a} | Moderate erythema | Moderate skin surface rise | A continuing ooze of red blood |
| 4 ^{b} | Severe (beet red) or damage to skin (eschar formation) | Severe skin surface rise | Significant bleeding from the sight |

 Table 1: Draize Scale for Skin Irritation

^{*a*} = Represents irritation in any category and may require participant's removal from the study based on PI decision.

Note: a rating of 1-3 on the skin irritation scale in any category may be recorded as an AE based on PI discretion.

 b = A rating of 4 on the skin irritation scale in any category must be recorded as AE and will require participant's removal from the treatment phase and/or study.

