9.0 ADVERSE EVENTS AND DEVICE DEFICIENCIES

9.1 Definitions of Events

9.1.1 Adverse Events (AEs)

An AE is defined as any untoward medical occurrence, unintended disease or injury, or untoward clinical signs (including abnormal laboratory findings) in participants, users or other persons, whether or not related to the investigational device and whether anticipated or unanticipated (ISO14155:2020). This definition includes events related to the investigational device, the comparator or the procedures involved.

Pre-existing conditions should be considered as part of the participant's medical history and should not be reported as an AE unless there is a substantial increase in severity or frequency of the condition, which has not been attributed to natural history. Likewise, planned hospital visits and/or hospital stays should not be considered as adverse events. Exacerbation of an existing condition should be reported as an AE if the event meets the protocol definition of an AE.

The clinical course of the event will be followed according to accepted standards of medical practice until the event resolves, stabilizes, or in the opinion of the Investigator, is no longer considered clinically significant. The Investigator must supply the Sponsor with information concerning the follow up and/or resolution of the AE.

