7.0 SAFETY ANALYSIS

Adverse Events (AEs) and Serious Adverse Events (SAEs) data will be presented based on treatment phases: the PureWick Phase includes all AEs/SAEs that occurred during the PureWick treatment phase, and the Hollister Phase includes all AEs/SAEs that occurred during the Hollister treatment phase. AEs/SAEs that occurred during the washout period will

RD	Statistical Analysis Plan	Page No. 18 of 20
	Study ID: UCC-8007	Version No: 01

be included in the analysis for the device used in Phase 1 treatment if treatment was performed for phase 1. If treatment was not performed in one of the phases, the AEs will be included in the other phase where treatment was performed for the subject.

Statistical Analysis Plan	Page No. 19 of 20
Study ID: UCC-8007	Version No: 01

INTERIM ANALYSIS PLAN 8.0

Not applicable.

REFERENCES 9.0

None.

10.0 **APPENDIX**

- Appendix 1 Appendix 2 Appendix 3
- Tables, Figures and Listing Shells Derived Data Specification Protocol Deviations: Major/Minor Classification

R D	Statistical Analysis Plan	Page No. 20 of 20
	Study ID: UCC-8007	Version No:
		01

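### Recording Draize scores of 1 to 3 as adverse events has no criterion, so the skin rows of the by-device AE table depend partly on an unblinded investigator's choice

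*Protocol*

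**What the plan says.** Protocol 7.3.1 sets two recording rules. At the top of the scale, "A rating of 4 on the skin irritation scale in any category must be recorded as AE". Below it, the text says "Any other score on the skin irritation scale in any category may be recorded as an AE based on PI discretion", and the note to Table 1 narrows this to "a rating of 1-3 on the skin irritation scale in any category may be recorded as an AE based on PI discretion". Neither place says how the discretion is to be used. Footnote a to the same table describes scores 1 to 3 thus: "Represents irritation in any category and may require participant's removal from the study based on PI decision".

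Protocol 9.1.1 gives the general definition: "An AE is defined as any untoward medical occurrence, unintended disease or injury, or untoward clinical signs". It applies whether or not the event is device-related or anticipated. Pre-existing conditions are left out unless they worsen substantially. Protocol 9.4 has every AE reported promptly to the sponsor.

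In the analysis, SAP 7.0 states that "Adverse Events (AEs) and Serious Adverse Events (SAEs) data will be presented based on treatment phases", one phase per device. The primary safety endpoint (Protocol 10.5.2, SAP 5.2.2.2) is separate. It is the mean of the daily Draize scores in each phase, for erythema, edema, bleeding and their sum, with paired differences.

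**The concern.** The general definition and the skin rule do not fit together. Irritation is listed in Protocol 2.5 as a potential adverse event of both devices, and the footnote calls scores 1 to 3 irritation. Yet whether such a finding enters the AE data is optional, even at score 3, which on the bleeding scale means blood that keeps oozing. The trial is open-label, so the person deciding knows which device was worn.

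What is at stake is the skin part of the AE table by device. The trial's rationale is to aid reimbursement in two countries, so readers are likely to take that table as a comparison of how often each device harms skin. If it rests on choice, it may disagree with the daily scores taken on the same women, and nothing in the SAP text explains or resolves the disagreement.

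**Working it through.** The plan states no AE rate, power or test for this point, so there is no figure to reproduce. The check is a comparison of texts, followed by an illustration.

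**1. Are scores of 1 to 3 new?** Protocol 7.2.6 bars a woman with a skin score above 0 from starting treatment that day, and drops her if 0 is not reached within 4 weeks. Section 7.2.17 repeats the procedures for phase 2, and 7.2.16 adds a re-screen of eligibility after washout. A score of 1 to 3 first seen after device use is therefore new in either phase, and the exclusion for pre-existing conditions does not cover it. A score that persists over several days is one episode, not one event per day.

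**2. How much data falls under the discretion?** Skin is scored on Days 2 to 30, which is 29 visits per phase. With about 30 women and full attendance, 30 × 2 × 29 = 1,740 assessments. Any score of 1 to 3 among them is recorded as an AE only if the investigator so decides.

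**3. Does another planned output count skin events?** In its text, the SAP gives phase means, per-subject daily plots, and each woman's maximum score as the axis of a boxplot against N-QoL (5.2.4.2). A mean does not show peaks. Over an illustrative 28 assessments, one day at score 3 gives 3/28 = 0.11, the same as three days at score 1. No table in the SAP text shows how many women reached each score on each device.

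**4. How far could recording alone move the AE table?** Let n women on each device truly have a score of 1 to 3, and let p be the share recorded as AEs. Expected recorded women = n × p, and the spurious difference between devices = n × (p1 − p2). All values below are assumptions, with no true difference between devices.

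| Affected per device | 50% v 50% | 60% v 40% | 80% v 40% |
|---|---|---|---|
| 6 | 3 v 3 | 3.6 v 2.4 | 4.8 v 2.4 |
| 10 | 5 v 5 | 6 v 4 | 8 v 4 |
| 15 | 7.5 v 7.5 | 9 v 6 | 12 v 6 |

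Equal recording gives a difference of zero at any n. Lower recording on both devices reduces the absolute counts but leaves the comparison level.

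**The case against.** The strongest reply is that skin harm is already compared without the investigator's discretion. The primary safety endpoint uses the daily scores directly, whether or not an AE form exists. That stands. A reader might infer that the primary safety comparison is compromised, but the documents do not support this, because AE forms are not an input to it.

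Second, a reader might infer that lenient and strict sites distort the device comparison. Each woman uses both devices, randomization is stratified by site, and the SAP fixes the block size at 2. The same site normally judges both devices, so site habits largely cancel. They still affect the absolute counts. Only recording that depends on the device would bias the comparison. The documents give no evidence that this would occur, though an unblinded investigator leaves it possible.

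Third, a reader might infer that every score of 1 to 3 must be an AE. The definition requires a sign to be untoward, which leaves room for judgement, above all at score 1, where redness is barely visible. Section 7.3.1 also gives a process: the nurse contacts the investigator or designee, and the site documents the assessment. What it lacks is a criterion, and the gap is harder to defend at score 3 than at score 1.

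Finally, SAP Appendix 1 (table shells) and Appendix 2 (derived data) are named but not reproduced, so a table by score may exist there.

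**Conclusion.** The inconsistency between Protocol 7.3.1 and Protocol 9.1.1 and 9.4 is real. The skin rows of the SAP 7.0 table depend partly on an unblinded choice with no stated criterion. The consequence is limited to that table and to disposition. Under 7.3.1 an AE unresolved within 4 weeks leads to discontinuation from the study, so two women with the same persisting score could be handled differently according to whether it was called an AE.

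The size of any bias is unknown. It is zero if recording is equal on both devices. With 10 affected women per device it is 2 women at 60% against 40% and 4 women at 80% against 40%, and these rates are assumptions only. In a descriptive pilot of about 30 women with no formal test and an unaffected primary safety endpoint, this is an inexpensive improvement to the safety reporting, not a flaw in the main comparison.

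**What to change.** In SAP 7.0, add a table derived from the daily Draize data, built the same way for both devices. It should give the number of women reaching each score (≥1, ≥2, ≥3, and 4), separately for erythema, edema and bleeding, with the first on-device day on which each score was reached. Show investigator-reported skin AEs beside it, and state that the derived table is the basis for comparing skin events between devices. State the time window of each column as well, because SAP 7.0 also assigns washout AEs to the phase 1 device. If Appendix 1 already holds such a table, a cross-reference and the statement of precedence are enough.

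Separately, the sponsor should reconcile 7.3.1 and its table notes with 9.1.1 and 9.4. Which recording rule applies is for the sponsor and its clinicians. Because a recorded AE can trigger the 4-week discontinuation rule, any change in recording may alter who leaves the study, and the two provisions should be considered together.

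The cost is one extra derived table from scores already collected, with no new forms or visits, plus the protocol wording. The nurse who scores the skin also knows the device, so the table removes investigator discretion from the count but not all open-label bias.
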